9.8.4 Sites performing correlative analysis

Dana-Farber Breast Tumor Immunology Lab (BTIL, [name], PhD)
Microbiome Dx

10. STUDY CALENDAR

Baseline evaluations are to be completed within 28 days prior to registration unless otherwise specified. Laboratory assessments, including pregnancy test, are to be completed within 14 days of registration. In the event that the participant's condition is deteriorating, laboratory evaluations should be repeated within 48 hours prior to initiation of the next cycle of therapy.

Assessments must be performed prior to administration of any study agent. Study assessments and agents should be administered within ± 3 days of the protocol-specified date, unless otherwise noted. Tumor assessments must be completed within ± 7 days of the protocol-specified date.

	Screening	Cycle 1		Cycle 2		Cycle 3	Cycle 4+		30 Day FUV ^k	Follow -Up
		D1	D15	D1	D28	D1	D1	D28		
Informed consent	X									
Demographics	X									
Medical history, including past lines of therapy	X									
Physical exam	X	X	X	X		X	X		X	
Vital signs ^a	X	X	X	X		X	X		X	
Height	X									
Weight	X	X		X		X	X		X	
Performance status	X	X		X		X	X		X	
Concurrent Meds	X	X	X	X		X	X		X	
AE Evaluation	X	X	X	X		X	X		X	
CBC w/diff ^f	X	X	X	X		X	X		X	
Serum chemistry ^b	X	X	X	X		X	X		X	
Serum cystatin C ^c	X	X	X	X		X	X		X	
B-HCG	X ^d									
Blood for ctDNA ^e		X				X			X	
Blood for genomic sequencing control		X								
Blood for plasma exosome analysis ^f		X	X	X		X			X	
Blood for germline DNA ^g		X								
Blood for PBMCs	X			X		X			X	
Archival tumor tissue	X									
Research stool collection and questionnaire ^m	X					X	X		X	
Research Biopsy	X			X						
EKG ^h	X									
Tumor assessments ⁱ	X				X			X	X ^{j,k}	
Abemaciclib		X-----X								
Survival Follow-up										X

Abemaciclib: 200mg po bid for 28 day cycles.

- a. Vital signs to include: diastolic and systolic blood pressure, heart rate and temperature
- b. Chemistry to include: Albumin, alkaline phosphatase, total bilirubin, bicarbonate, BUN, calcium, chloride, creatinine, glucose, potassium, total protein, SGOT [AST], SGPT [ALT], sodium.
- c. Cystatin C should be performed each time serum chemistries are performed, as abemaciclib is known to compete for tubular secretion of creatinine, causing an increase in serum creatinine which does not reflect changes in renal function. Cystatin C allows for more accurate assessment of renal function in this context.
- d. Serum pregnancy test (women of childbearing potential as defined in the eligibility section)
- e. ctDNA to be drawn at C1D1, each restaging visit and at time of progression/30 Day FUV (Streck)
- f. Plasma to be drawn at C1D1, C1D15, C2D1, C3D1 and at time of progression/30 Day FUV (EDTA)

- g. Blood drawn at C1D1 for collection of germline DNA (Streck)
- h. EKGs to be done at Screening and if clinically indicated
- i. Tumor assessments will be performed every 2 cycles (8 weeks) for the first 6 cycles (6 months) and then every 3 cycles (12 weeks) going forward.
- j. Tumor assessments should be obtained at 30 day FUV if not done within the previous 8 weeks
- k. Follow-up survival (disease status and overall status) follow-up evaluation – a separate clinic visit is not required, this can be done over the phone every six months.
- l. 30 Day FUV to be completed within 30 days of last dose of abemaciclib
- m. Research stool collection to occur at baseline, between C2D1 and C3D1, at the time of grade ≥ 2 diarrhea, and at the end of treatment or progression, whichever occurs first.

11. MEASUREMENT OF EFFECT

11.1 Antitumor Effect – Solid Tumors

A baseline tumor evaluation must be performed within 4 weeks before patient begins study treatment. Restaging scans will be performed every 8 weeks.

Response and progression will be evaluated in this study using the international criteria proposed by the New Response Evaluation Criteria in Solid Tumors (RECIST): Revised RECIST Guideline (version 1.1; Eisenhauer et al. 2009). Changes in the largest diameter (unidimensional measurement) of the tumor lesions and the shortest diameter in the case of malignant lymph nodes are used in the RECIST criteria.

11.1.1 Definitions

Evaluable for Target Disease response. Only those participants who have measurable disease present at baseline, have received at least one cycle of therapy, and have had their disease re-evaluated will be considered evaluable for target disease response. These participants will have their response classified according to the definitions stated below. (Note: Participants who exhibit objective disease progression prior to the end of cycle 1 will also be considered evaluable.)

Evaluable Non-Target Disease Response. Participants who have lesions present at baseline that are evaluable but do not meet the definitions of measurable disease, have received at least one cycle of therapy, and have had their disease re-evaluated will be considered evaluable for non-target disease. The response assessment is based on the presence, absence, or unequivocal progression of the lesions.

11.1.2 Disease Parameters

Tumor lesions/lymph nodes will be categorized at baseline as measurable or non-measurable. Measurable disease is defined by the presence of at least 1 measurable lesion.

11.1.2.1 Measurable

Tumor lesions: Measured in at least 1 dimension (longest diameter in the plane of

measurement is to be recorded) with a minimum size of:

- 10 mm by computed tomography (CT) or magnetic resonance imaging (MRI) scan (slice thickness ≤ 5 mm)
- 10 mm caliper measurement by clinical exam (non-measurable lesions if cannot be accurately measured with calipers)
- 20 mm by chest X-ray.

Malignant lymph nodes: To be considered pathologically enlarged and measurable, a lymph node must be ≥ 15 mm in short axis when assessed by CT scan (CT scan slice thickness recommended to be ≤ 5 mm).

11.1.2.2 Nonmeasurable

All other lesions, including small lesions (longest diameter < 10 mm or pathological lymph nodes with ≥ 10 to < 15 mm short axis) as well as truly non-measurable lesions. Lesions considered truly non-measurable include: leptomeningeal disease, ascites pleural/pericardial effusions, lymphangitis cutis/pulmonis, inflammatory breast disease, lymphangitis involvement of skin or lung, abdominal masses/abdominal organomegaly identified by physical exam that is not measurable by reproducible imaging techniques.

11.1.2.3 Special Considerations for Lesion Measurability

Bone lesions:

- Bone scan, PET scan or plain films are not considered adequate imaging techniques to measure bone lesions.
- Lytic bone lesions or mixed lytic-blastic lesions, with identifiable soft tissue components, that can be evaluated by cross sectional imaging techniques such as CT or MRI, can be considered measurable lesions if the soft tissue component meets the definition of measurability.
- Blastic bone lesions are non-measurable.

Cystic Lesions:

- Simple cysts should not be considered as malignant lesions (neither measurable nor nonmeasurable)
- Cystic lesions thought to represent cystic metastases can be considered as measurable lesions, if they meet the definition of measurability. If non-cystic lesions are presented in the same patients, these are preferred for selection as target lesions.

Lesions with Prior Local Treatment:

- Tumor lesions situated at a previously irradiated area, or in an area subjected to other loco-regional therapy, are non-measurable unless there has been demonstrated progression in the lesion.

11.1.3 Target lesions

When more than 1 measurable lesion is present at baseline, all lesions up to a maximum of 5 lesions total (and a maximum of 2 lesions per organ) representative of all involved organs should be identified as target lesions and will be recorded and measured at baseline. Non-nodal target lesions should be selected on the basis of their size (lesions with the longest diameter), be representative of all involved organs, and can be reproduced in repeated measurements. Measurable lymph nodes are target lesions if they meet the criteria of a short axis of ≥ 15 mm by CT scan. All measurements are to be recorded in the case record form (CRF) in millimeters (or decimal fractions of centimeters [cm]).

11.1.4 Non-target lesions.

All other lesions (or sites of disease) are identified as non-target lesions (chosen based on their representativeness of involved organs and the ability to be reproduced in repeated measurements) and should be recorded at baseline. Measurement of these lesions are not required but should be followed as 'present,' 'absent,' or in rare cases 'unequivocal progression.' In addition, it is possible to record multiple non-target lesions involving the same organ as a single item on the CRF (for example, multiple liver metastases recorded as 1 liver lesion).

Lymph nodes with short axis ≥ 10 mm but < 15 mm should be considered non-target lesions. Nodes that have a short axis < 10 mm are considered non-pathological and are not recorded or followed.

11.1.5 Methods for Evaluation of Disease

All measurements should be taken and recorded in metric notation using a ruler, calipers, or a digital measurement tool. All baseline evaluations should be performed as closely as possible to the beginning of treatment and never more than 4 weeks before the beginning of the treatment.

The same method of assessment and the same technique should be used to characterize each identified and reported lesion at baseline and during follow-up. Imaging-based evaluation is preferred to evaluation by clinical examination unless the lesion(s) being followed cannot be imaged but are assessable by clinical exam.

An adequate volume of a suitable contrast agent should be given so that the metastases are demonstrated to best effect and a consistent method is used on subsequent examinations for any given patient. If prior to enrollment it is known a patient is not able to undergo CT scans with IV contrast due to allergy or renal insufficiency, the decision as to whether a non-contrast CT or MRI (with or without IV contrast) should be used to evaluate the patient at baseline and follow-up should be guided by the tumor type under investigation and the anatomic location of the disease.

Clinical lesions. Clinical lesions will only be considered measurable when they are superficial (e.g., skin nodules and palpable lymph nodes) and ≥ 10 mm in diameter as assessed using calipers (e.g., skin nodules). In the case of skin lesions, documentation by

color photography, including a ruler to estimate the size of the lesion, is recommended. When lesions can be evaluated by both clinical exam and imaging, imaging evaluation should be undertaken since it is more objective and may be reviewed at the end of the study.

Chest x-ray. Chest CT is preferred over chest X-ray when progression is an important endpoint. Lesions on chest X-ray may be considered measurable if they are clearly defined and surrounded by aerated lung.

Conventional CT and MRI. CT scan is the best currently available and reproducible method to measure lesions selected for response assessment. Measurability of lesions on CT scan is based on the assumption that CT slice thickness is ≤ 5 mm. When CT scan have slice thickness > 5 mm, the minimum size for a measurable lesion should be twice the slice thickness. MRI is also acceptable in certain situations (for example, for body scans). If there is concern about radiation exposure at CT, MRI may be used instead of CT in selected instances.

Pet Scan (FDG-PET, PET CT): PET is not recommended for lesion assessment. If a new lesion is found by PET, another assessment must be done by CT, unless the PET CT is of diagnostic quality. If CT is done to confirm the results of the earlier PET scan, the date of progression must be reported as the earlier date of the PET scan.

Ultrasound. Ultrasound should not be used to measure lesion size. Ultrasound examinations cannot be reproduced in their entirety for independent review at a later date and, because they are operator dependent, it cannot be guaranteed that the same technique and measurements will be taken from one assessment to the next. If new lesions are identified by ultrasound in the course of the study, confirmation by CT or MRI is advised.

Endoscopy, Laparoscopy. The utilization of these techniques for objective tumor evaluation is not advised. However, such techniques may be useful to confirm complete pathological response when biopsies are obtained or to determine relapse in trials where recurrence following complete response (CR) or surgical resection is an endpoint.

Tumor markers. Tumor markers alone cannot be used to assess response. If markers are initially above the upper normal limit, they must normalize for a participant to be considered in complete clinical response. Specific guidelines for both CA-125 response (in recurrent ovarian cancer) and PSA response (in recurrent prostate cancer) have been published [JNCI 96:487-488, 2004; J Clin Oncol 17, 3461-3467, 1999; J Clin Oncol 26:1148-1159, 2008]. In addition, the Gynecologic Cancer Intergroup has developed CA-125 progression criteria which are to be integrated with objective tumor assessment for use in first-line trials in ovarian cancer [JNCI 92:1534-1535, 2000].

Cytology, Histology. These techniques can be used to differentiate between partial responses (PR) and complete responses (CR) in rare cases (e.g., residual lesions in tumor types, such as germ cell tumors, where known residual benign tumors can remain).

When effusions are known to be a potential adverse effect of treatment (for example, with certain taxane compounds or angiogenesis inhibitors), the cytological confirmation the neoplastic origin of any effusion that appears or worsens during treatment can be considered if the measurable tumor has met criteria for response or stable disease (SD) in order to differentiate between response (or SD) and progressive disease (PD).

Bone Scan: If lesions measured by bone scan are reported at baseline, it is necessary to repeat the bone scan when trying to identify a complete response (CR) or partial response (PR) in target disease or when progression in bone is suspected.

11.1.6 Response Criteria

11.1.6.1 Evaluation of Target Lesions:

Complete Response (CR): Disappearance of all target lesions. Any pathological lymph nodes (whether target or non-target) must have reduction in short axis to <10 mm.

Partial Response (PR): At least a 30% decrease in the sum of the diameters of target lesions, taking as reference the baseline sum diameters.

Progressive Disease (PD): At least a 20% increase in the sum of the diameters of target lesions, taking as reference the smallest sum on study (this includes the baseline sum if that is the smallest on study). In addition to the relative increase of 20%, the sum must also demonstrate an absolute increase of at least 5 mm. The appearance of one or more new lesions is also considered progressions.

Stable Disease (SD): Neither sufficient shrinkage to qualify for PR nor sufficient increase to qualify for PD, taking as reference the smallest sum diameters while on study.

Not Evaluable: When an incomplete radiologic assessment of target lesions is performed or there is a change in the method of measurement from baseline that impacts the ability to make a reliable evaluation of response.

11.1.6.2 Evaluation of Non-Target Lesions

Complete Response (CR): Disappearance of all non-target lesions and normalization of tumor marker level. All lymph nodes must be non-pathological in size (<10 mm short axis).

Non-CR/Non-PD: Persistence of one or more non-target lesion(s) and/or maintenance of tumor marker level above the normal limits.

Progressive Disease (PD): Appearance of one or more new lesions and/or

unequivocal progression of existing non-target lesions.

Not Evaluable: When a change in method of measurement from baseline occurs and impacts the ability to make a reliable evaluation of response.

11.1.6.3 Evaluation of New Lesions

The finding of a new lesion should be unequivocal (i.e. not due to difference in scanning technique, imaging modality, or findings thought to represent something other than tumor (for example, some ‘new’ bone lesions may be simply healing or flare of pre-existing lesions). However, a lesion identified on a follow-up scan in an anatomical location that was not scanned at baseline is considered new and will indicate PD. If a new lesion is equivocal (because of small size etc.), follow-up evaluation will clarify if it truly represents new disease and if PD is confirmed, progression should be declared using the date of the initial scan on which the lesion was discovered.

11.1.6.4 Evaluation of Best Overall Response

The best overall response is the best response recorded from the start of the study treatment until the earliest of objective progression or start of new anticancer therapy, taking into account any requirement for confirmation. The patient’s best overall response assignment will depend on the findings of both target and non-target disease and will also take into consideration the appearance of new lesions. The Best Overall Response will be calculated via an algorithm using the assessment responses provided by the investigator over the course of the trial.

11.1.6.5 Time Point Response

It is assumed that at each protocol-specified time point, a response assessment occurs. (When no imaging/measurement is done at all at a particular time point, the patient is not evaluable (NE) at that time point.) Table 11.1.4.5 provides a summary of the overall response status calculation at each time point for patients who have measurable disease at baseline.

Table 11.1.4.5 Time Point Response: Patients with Target (+/- Nontarget) Disease

Target Lesions	Non-Target Lesions	New Lesions	Overall Response	Best Overall Response when Confirmation is Required
CR	CR	No	CR	≥4 wks Confirmation
CR	Non-CR/Non-PD	No	PR	≥4 wks Confirmation
CR	Not evaluated	No	PR	

PR	Non-CR/Non-PD/not evaluated	No	PR	
SD	Non-CR/Non-PD/not evaluated	No	SD	Documented at least once ≥ 4 wks from baseline
PD	Any	Yes or No	PD	no prior SD, PR or CR
Any	PD*	Yes or No	PD	
Any	Any	Yes	PD	
Not all evaluated	Non-PD	No	SD	

Abbreviations: CR = complete response; PR = partial response; SD = stable disease; PD = progressive disease; NE = inevaluable.

* In exceptional circumstances, unequivocal progression in non-target lesions may be accepted as disease progression.

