11.1.7 Duration of Response

Duration of overall response: The duration of overall response is measured from the time measurement criteria are met for CR or PR (whichever is first recorded) until the first date that recurrent or progressive disease is objectively documented (taking as reference for progressive disease the smallest measurements recorded since the treatment started, or death due to any cause. Participants without events reported are censored at the last disease evaluation).

Duration of overall complete response: The duration of overall CR is measured from the time measurement criteria are first met for CR until the first date that progressive disease is objectively documented, or death due to any cause. Participants without events reported are censored at the last disease evaluation.

Duration of stable disease: Stable disease is measured from the start of the treatment until the criteria for progression are met, taking as reference the smallest measurements recorded since the treatment started, including the baseline measurements.

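### Table 11.1.4.5 calls an incomplete target-lesion assessment stable disease while Section 11.1.6.1 calls it Not Evaluable, so DCR and CBR can credit patients who never had a complete post-baseline target assessment

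*Combined protocol and SAP*

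**What the plan says.** Section 11.1.6.1, on target lesions, has this category: "Not Evaluable: When an incomplete radiologic assessment of target lesions is performed". The same entry also covers a change of measurement method that undermines a reliable evaluation.

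Section 11.1.6.5 introduces Table 11.1.4.5 as the rule for overall response; it "provides a summary of the overall response status calculation at each time point" for patients with measurable disease. The last row is "Not all evaluated Non-PD No SD", with no condition in the confirmation column. The only NE rule in that section covers a wholly missed visit: "When no imaging/measurement is done at all at a particular time point, the patient is not evaluable (NE) at that time point". NE is in the table's abbreviation list, but no row produces it.

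Three other provisions carry the label onward:

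- Section 11.1.6.4: "The Best Overall Response will be calculated via an algorithm using the assessment responses provided by the investigator".
- The complete-SD row of the table: "Documented at least once ≥ 4 wks from baseline".
- Section 11.1.7: "Stable disease is measured from the start of the treatment until the criteria for progression are met".

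Section 13.4 counts SD of at least 16 weeks in DCR and SD of at least 24 weeks in CBR. It makes disease control the main outcome for evaluating phospho-Rb reduction.

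**The concern.** One visit gets two incompatible labels. Under 11.1.6.1 a partial target assessment gives no usable target result. Under the table it gives SD, provided nothing else shows progression. Because the table sets the overall response, SD is the label that reaches best overall response.

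Nothing in Sections 11 or 13 requires a complete target assessment before SD is assigned or counted. Section 11.1.1 asks only that disease was re-evaluated, and Section 13.6.2 makes every treated patient evaluable for efficacy. A patient whose target lesions were never fully measured after baseline can thus be counted as controlled on missing information.

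At stake are DCR, CBR and the phospho-Rb comparison. If the conflict stays, whoever programs the response algorithm chooses between SD and NE, possibly with outcomes already visible in an open, single-arm study.

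**Working it through.** **1. A patient on the plan's calendar.** Section 10 places tumor assessments on Day 28 of cycles 2, 4 and 6. Elapsed days from Cycle 1 Day 1 to Day 28 of cycle n are 28n − 1:

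- cycle 2: 28 × 2 − 1 = 55
- cycle 4: 28 × 4 − 1 = 111
- cycle 6: 28 × 6 − 1 = 167

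The thresholds are 16 × 7 = 112 days (DCR) and 24 × 7 = 168 days (CBR).

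Suppose target assessments are incomplete at days 55 and 111, with no non-target progression and no new lesion, and PD is found at day 167.

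| Rule | Day 55 | Day 111 | Day 167 | Best response | Disease control? |
|---|---|---|---|---|---|
| Table 11.1.4.5, last row | SD | SD | PD | SD, 167 days | Yes (167 ≥ 112) |
| 11.1.6.1 carried to overall response | NE | NE | PD | PD | No |

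If the day-167 assessment is also incomplete and PD comes later, the table counts the patient in CBR too. Two cases miss a threshold by one day: PD at day 111 for DCR (112 needed) and PD at day 167 for CBR (168 needed). They turn on how days are counted and on the window: "Tumor assessments must be completed within ± 7 days of the protocol-specified date".

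**2. Effect on DCR.** Section 13.2 gives 37 evaluable patients and Section 13.4 an anticipated DCR of 34%. With k such patients the rate is 0.34 + k/37:

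- k = 0: 34.0%
- k = 1: 0.34 + 0.027 = 36.7%
- k = 2: 0.34 + 0.054 = 39.4%

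With all 38 treated patients as denominator, each one adds 1/38 = 2.6 points. The values of k are assumptions.

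**3. Effect on the phospho-Rb comparison.** Inputs from Section 13.4: two-sided Fisher exact test at 0.05, 60% with reduction, DCR 53.3% against 5%. Power is the sum of the two binomial probabilities over all tables with p ≤ 0.05.

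*Plan's figures first.* With 33 pairs split 20 and 13, power is 85.4% (plan: 85%). With 29 pairs split 17 and 12, it is 80.9% (plan: 81%). Both reproduce.

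*One such patient per 37.* The overall DCR rises by d = 1/37 = 0.027. The result depends on where that patient falls:

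| Allocation | DCR with reduction | DCR without reduction | Power, 20 vs 13 | Power, 17 vs 12 |
|---|---|---|---|---|
| Even over non-controlled patients, m = d/0.66 = 0.041 | 0.533 + 0.041 × 0.467 = 55.2% | 0.05 + 0.041 × 0.95 = 8.9% | 77.8% | 70.4% |
| In proportion to group DCR, factor 1 + d/0.34 = 1.079 | 0.533 × 1.079 = 57.5% | 0.05 × 1.079 = 5.4% | 90.2% | 85.5% |
| All with reduction | 0.533 + d/0.6 = 57.8% | 5.0% | 91.3% | 87.0% |
| All without reduction | 53.3% | 0.05 + d/0.4 = 11.8% | 65.1% | 56.9% |

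At two per 37, the first two allocations give 70.5% and 93.7% at 20 vs 13. The direction is therefore not fixed.

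**4. Primary endpoint.** SD and NE are both non-responses, so confirmed ORR and the two-stage rule do not change.

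**The case against.** The strongest reply is that the two passages work at different levels. Section 11.1.6.1 classifies target lesions; the table combines target, non-target and new-lesion findings into an overall response. Strictly, 11.1.6.1 assigns no overall NE. That is correct, and the second row of the worked example carries the target label up. But the distinction restates the problem: the table turns a target result that the protocol calls Not Evaluable into an overall SD.

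Other points have some weight:

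- The reliability qualifier in 11.1.6.1 may also govern incomplete assessments, so that some partial assessments remain evaluable. Even so, those that do prevent a reliable evaluation are Not Evaluable there and SD in the table.
- DCR and CBR are defined per RECIST 1.1, and Section 11.1.8 plans central measurement. Neither says which of the two written rules governs.
- The four-week note is printed on the complete-SD row, and the last row's cell is blank. Applying the note there would add a timing condition but would not require a complete assessment.
- NE is listed among the abbreviations but appears in no row, so the entry may be a drafting slip. That is a reason to check and correct the cell.

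The limits on weight stand: these are secondary endpoints without a decision rule, and the frequency is unknown.

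**Conclusion.** The concern holds. Followed as written, the table can credit disease control or clinical benefit to a patient with no complete target assessment between baseline and progression, in conflict with Section 11.1.6.1.

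The size is 2.7 points of DCR or CBR per affected patient. The number affected is an assumption and may be zero, and some of these patients may have been truly stable, so not every one is a false positive. The power range shows how sensitive a comparison of 33 pairs is to a single classification; it does not predict a loss. The point should be corrected, but it does not threaten the primary conclusion.

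**What to change.** Change the overall response in the last row of Table 11.1.4.5 from SD to NE, to match Section 11.1.6.1. Add one sentence to the DCR and CBR definitions in Section 13.4: SD must rest on at least one evaluable (not NE) post-baseline assessment, and PD is still called when the lesions that were assessed already meet the criteria for PD.

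The cost is one cell and one sentence. The planned power figures stay as they are. DCR and CBR may come out slightly lower, because some patients who were stable but incompletely imaged will no longer count.

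The change does not require a complete assessment near week 16 or week 24. A patient with evaluable SD at week 8, an incomplete assessment at week 16 and PD at week 24 would still count as disease control.
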